## 8. Laboratory signs

Patients with at least one blood test laboratory result out of range will be considered as patients with laboratory signs.

- For creatinine, patients with a value lower than 45 µmol/L or higher than 104 µmol/L will be considered as out of range
- For haemoglobin, patients with a value lower than 11,5 g/dL or higher than 16. g/dL will be considered as out of range
- For BNP, patients with a value higher than 100 pg/mL will be considered as out of range
- For NTproBNP, patients with a higher than 125 pg/mL will be considered as out of range
- For Troponin I, patients with a value higher than 26 pg/mL will be considered as out of range

- For Troponin T, patients with a value higher than 14 pg/mL will be considered as out of range

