## Variables– include exposures, outcomes, and key co-variables

- Date Informed Consent Document signed.
- Inclusion and exclusion criteria met.
- Patient demographic data (Age, Gender, Weight, Height, Race).

- Patient family history.
  - Relatives (parents, siblings and 2nd/3rd grade family) with known cardiomyopathy (CM), Polyneuropathy (PN), and/or Sudden cardiac death (SCD).
- Patient medical history.
- Results of Cardiological assessments, if performed.
  - Blood pressure
  - Bone scintigraphy with radiolabelled Technetium tracer (99mTc-DPD or 99mTc-PYP or 99mTc-HMDP) visual grading score and/or SPECT
  - ECG (last ECG performed).
  - Echocardiography.
  - Magnetic resonance imaging (MRI).
- Neurological assessments:
  - Symptoms and clinical signs of peripheral neuropathy (small fibres).
  - Autonomic symptoms and clinical signs.
  - Carpal tunnel syndrome (CTS) history and symptoms.

Additional set of variables from the patient clinical records as available will be included in the CRF of those patients with cardiac fixation in bone scintigraphy (Grade 1, 2 or 3) and/or SPECT:

- Results from blood sample testing (Creatinine, Haemoglobin, BNP, NT proBNP, Troponin I & T);
- Results from monoclonal protein studies (in urine and blood);
- Results from *TTR* gene sequencing.

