### **9.9.4. Measurement Biases**

The assessment of the primary endpoint is based on the bone scintigraphy reading, which implies an evaluator-dependent variability and may create a bias.

In order to measure this bias scintigraphy reviews by external evaluators have been planned. Digitalized images will be reviewed by two external evaluators to analyze level of concordance/discrepancies among different specialists as part of a secondary objective for the study.

Secondary endpoints are based on laboratory analyses and may constitute a bias as each site has their own process, units and norms. They are also based on symptom assessment that may differ from an investigator to another and may constitute a bias.

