### **6.4 COVARIATES**

- Grade (0, 1, 2, 3) and for grade 2&3 pooled together
- Age in class 50 – ≤60 ; >60 – ≤70 years ; >70 – ≤80 years ; > 80 years]
- Gender (Male/Female)
- Cardiological symptomatology (Yes/No, where patient with a cardiological symptomatology are defined as patient with a least one cardiological manifestation (point 7 in 0)
- High Creatinine, high BNP and high NTproBNP (See Section 6.3, § 8)

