### 2) Impact of protocol amendment 2 – No longer using a centralized lab

The prevalence of patients with laboratory signs will be calculated in patients included before protocol amendment and in patients included after protocol amendment (Amendment 2 – Date: 11-Feb-2020). The percentage and its 95% CI will be provided.

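### The check on losing the central laboratory rests on one any-of-six composite that moves with the number of tests done, so a before/after difference cannot be attributed to the laboratory

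*SAP*

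**What the plan says.** The panel is listed in the Protocol abstract under variables: "Results from blood sample testing (Creatinine, Haemoglobin, BNP, NT proBNP, Troponin I & T". These results are taken from clinical records where they exist, and only for patients with cardiac fixation. Protocol 9.2.2 repeats that laboratory results enter the CRF if available.

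SAP 6.3, item 8, turns the panel into a yes/no endpoint: "Patients with at least one blood test laboratory result out of range will be considered as patients with laboratory signs". BNP, NT-proBNP and the two troponins have an upper limit only. The other two analytes are two-sided: "For creatinine, patients with a value lower than 45 µmol/L or higher than 104 µmol/L will be considered as out of range", and "For haemoglobin, patients with a value lower than 11,5 g/dL or higher than 16. g/dL will be considered as out of range". A low creatinine alone, or a high haemoglobin alone, therefore makes a patient positive.

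SAP 7 leaves missing values missing. SAP 8.1 bases percentages on filled data. Neither section says how to classify a patient with some tests missing and none abnormal.

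SAP section 1 records that version 2 added a sensitivity analysis on the loss of the central laboratory. SAP 8.2, sensitivity analysis 2, defines it: "The prevalence of patients with laboratory signs will be calculated in patients included before protocol amendment", and likewise for patients included afterwards, each with a 95% CI. It plans no result by analyte, no count of tests done and no adjustment.

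**The concern.** An any-one rule gives a patient with six results six chances to be positive, and a patient with one result a single chance. When testing follows routine care, the composite mixes how abnormal patients are with how thoroughly they were tested.

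This matters most in sensitivity analysis 2. Its purpose is to show whether moving from a central laboratory to local ones changed the laboratory findings. The amendment table in Protocol section 5 says that Amendment 2 also removed biological sample collection, so the number of tests per patient may have changed at the same date. A difference could then appear with no laboratory effect. If one analyte is abnormal in nearly everyone, the opposite happens: a real shift in another analyte barely moves the composite. In neither case could a reader draw the conclusion that the analysis was added to support.

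**Working it through.** **Figures in the plan.** The documents give no figure for laboratory signs or for the before/after comparison. The nearest is the precision for any sign in Protocol 9.5: 10% of 1500 is 150 patients, and 1.96 × √(0.30 × 0.70 / 150) = 0.0733, which reproduces the stated ±7.3%. No stated figure is wrong on this point.

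**Inputs.** From the documents: six analytes, the any-one rule, collection as available, no imputation, and a composite-only comparison by period. Assumed, because the documents do not say: the chance p that one test is out of range, the number k of tests per patient, and the correlation between tests.

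**Step 1: dependence on the number of tests.** With independent tests, P(at least one out of range) = 1 − (1 − p)^k. For example, 1 − 0.8^6 = 0.738 and 1 − 0.7^6 = 0.882. The correlated columns come from a simulation with a Gaussian copula and correlation 0.6.

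| p per test | k = 1 | k = 3, independent | k = 6, independent | k = 3, corr. 0.6 | k = 6, corr. 0.6 |
|---|---|---|---|---|---|
| 10% | 10% | 27.1% | 46.9% | 20.5% | 29.2% |
| 20% | 20% | 48.8% | 73.8% | 36.7% | 48.1% |
| 30% | 30% | 65.7% | 88.2% | 50.4% | 62.4% |

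Correlation weakens the dependence but does not remove it.

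**Step 2: a difference without a laboratory effect.** Suppose, for illustration, six tests per patient before Amendment 2 and three after, with the same p in both periods.

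- Independent tests: 46.9 − 27.1 = 19.8 points at p = 10%, 73.8 − 48.8 = 25.0 at 20%, and 88.2 − 65.7 = 22.5 at 30%.
- Correlation 0.6: 29.2 − 20.5 = 8.7, 48.1 − 36.7 = 11.4, and 62.4 − 50.4 = 12.0 points.

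Take 75 patients per period (150 split evenly, an assumption) and p = 20%. Under independence the Wilson 95% intervals are 62.8–82.4% and 37.8–59.9%, which do not overlap. With correlation 0.6 they are about 37.2–59.2% and 26.7–48.0%, which do overlap.

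**Step 3: a laboratory effect without a difference.** Suppose creatinine, haemoglobin and NT-proBNP are measured, independent, with NT-proBNP out of range in 95% (assumed).

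- Creatinine 30%, haemoglobin 20%: 1 − 0.70 × 0.80 × 0.05 = 97.2%.
- Creatinine 45%, haemoglobin 35%: 1 − 0.55 × 0.65 × 0.05 = 98.2%.

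A rise of 15 points in each of two analytes moves the composite by 1 point.

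**Step 4: partly filled panels.** Consider a patient with one normal creatinine and five missing tests. Counted as negative, this patient pulls the prevalence down on thin evidence. Counted as missing, every partly tested patient left in the denominator is positive by construction. The SAP does not choose between these readings.

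**The case against.** Much of the per-analyte reporting is already planned. SAP 8.2, Other analyses, item 3, describes all CRF variables, and SAP 8.1 gives filled and missing counts for each. This stands, but those descriptions are by grade, number of red flags and genotype, not by period, so they do not serve sensitivity analysis 2.

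The study makes no inferential claim (SAP 4.1 and 4.2), laboratory values exist only for scan-positive patients, and the regressions comparing them with negative patients exclude laboratory values. This also stands, and it keeps the point small.

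The magnitudes are assumed, and full independence is implausible: BNP and NT-proBNP are related markers, as are the two troponins. That is why the correlated results are shown. The two harms also do not act together: near the ceiling the number of tests matters little, and where it matters the composite is not near the ceiling. The documents do not say which case applies.

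Three stronger readings are tempting, and the documents do not support them.

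- A reader might infer from SAP 6.4, which lists "High Creatinine, high BNP and high NTproBNP", that the other directions are irrelevant and the two-sided limits an error. That section is a covariate list. It gives no direction for haemoglobin or the troponins, and a descriptive endpoint need not match it.
- A reader might take the admission in Protocol 9.9.4 that "each site has their own process, units and norms" as showing that one fixed limit per analyte is wrong. The protocol discloses this as a limitation, and a common limit is a defensible way to harmonise sites.
- A reader might conclude that the analysis can show nothing, or that testing certainly fell after Amendment 2. The comparison can show a change, though not its cause. The earlier panel is not described, so a fall in tests per patient is only an inference.

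SAP Appendix 1 leaves abnormal values to medical advice. Revised limits would not settle the any-one rule or the partly filled panel.

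**Conclusion.** The concern holds in a limited form. Sensitivity analysis 2 judges the loss of the central laboratory only through an any-one-of-six composite, built on results collected as available and with no rule for partly filled panels. A before/after difference in it cannot be attributed to the laboratory change, and a near-ceiling value could hide a real shift. The dependence on testing follows from the rule itself. Its size does not: per-test rates, tests per patient and correlation are all assumed. Within the ranges shown, halving the tests from six to three moves the composite by about 9 to 25 points with nothing else changed. The primary objective and the stated precision are not affected. This is a worthwhile refinement to one sensitivity analysis, not a flaw in the study's main result.

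**What to change.** In SAP 8.2, sensitivity analysis 2, report each of the six analytes before and after Amendment 2. Show low and high results apart for creatinine and haemoglobin, use the number of patients tested as denominator, and give a 95% CI by the Wilson method already named in SAP 8.1. Add the distribution of the number of tests per patient in each period.

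Keep the composite as a descriptive figure. Show it by number of analytes tested, and report patients with a partly filled panel and no abnormal result as a separate category. Do not restrict it to patients with a minimum panel: in routine care, more fully tested patients may differ from the rest, and that would replace one bias with another.

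The cost is a few extra table rows from data already collected.

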### **9. Coexistence of typical neurological signs / symptoms**

Patients with only one redflag / patients with two redflags / patients with at least three redflags.

### **6.4 COVARIATES**

- Grade (0, 1, 2, 3) and for grade 2&3 pooled together
- Age in class 50 – ≤60 ; >60 – ≤70 years ; >70 – ≤80 years ; > 80 years]
- Gender (Male/Female)
- Cardiological symptomatology (Yes/No, where patient with a cardiological symptomatology are defined as patient with a least one cardiological manifestation (point 7 in 0)
- High Creatinine, high BNP and high NTproBNP (See Section 6.3, § 8)

### **7 HANDLING OF MISSING VALUES**

Missing data will not be imputed.

## **8 STATISTICAL METHODOLOGY AND STATISTICAL ANALYSES**

### **8.1 STATISTICAL METHODS**

Quantitative variables will be described using number of filled and missing data, mean, standard deviation, median, 1st and 3rd quartiles, minimum and maximum. The 95%CI of the mean will also be provided, assuming a normal distribution. In case of departure from normality, results will be interpreted based on median and Interquartile Range (IQR).

Qualitative variables will be described using number of filled and missing data and, for each modality, the frequency and percentage (referring to filled data). A 95% confidence interval (CI) will be associated to binomial proportions using the Wilson score method.

Factors associated to an outcome of interest (ATTR vs other and ATTRwt vs ATTRv within patients diagnosed with ATTR-CM) will be identified using univariate logistic regression models. A separate logistic regression model will be created for each factor (as well as covariates described in section 6.4). If the variable is significantly associated to the outcome at the 10% level then the factor will be put forward into a multivariate model. Once the univariate model selection is complete, backwards selection will be used to remove factors from the multivariate model which do not have a significant p value at the 5% level. The covariate with the highest p value will be removed in turn until all factors have a p value less than 0.05. If a significant interaction is found then the individual factors of this interaction will be kept in the model, regardless of their p value. A significant interaction is tested for between all variables in the multivariate model.

Furthermore, a table showing all of the 95% confidence intervals and p values for the odds ratios coming from the univariate and multivariate models will be created.

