**Figure 1. Diagnostic Algorithm for Patients with Suspected Amyloid Cardiomyopathy (Gillmore 2016)**

Echocardiographic features suggesting/indicating cardiac amyloid include (but are not limited to) increased left ventricular wall thickness, restrictive filling pattern, abnormal left and right ventricular longitudinal strain, and atrial septal thickening.

Features suggesting/indicating cardiac amyloid on cardiac magnetic resonance imaging (CMR) include (but are not limited to) restrictive morphology, abnormal gadolinium kinetics, and extracellular volume expansion based on T1 mapping.

AApoA1 indicates apolipoprotein A-I; DPD, 3,3-diphosphono-1,2-propanodicarboxylic acid; HDMP, hydroxymethylene diphosphonate; and PYP, pyrophosphate.

Moreover, the data clearly indicate that the combined finding of grade 2 or 3 cardiac uptake on radionuclide scintigraphy and the absence of a monoclonal protein by serum immunofixation electrophoresis (IFE), urine IFE, and sFLC (Freelite) assay was 100% specific for presence of ATTR-CM (Gillmore 2016).

A diagnosis of ATTR-CM should be followed by TTR genotyping in all patients to differentiate between wild-type and variant ATTR-CM.

The main purpose of this study is to determine the prevalence of ATTR-CM among patients admitted due to LVH of unknown etiology when radionuclide bone scintigraphy or SPECT is used.

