#### **9.2.4. Blood Samples Analyses**

Following the standard practice guidelines for the patient population with positive scintigraphy, blood and urine analyses are usually done to rule out AL amyloidosis. If performed, results of these tests will be collected.

Moreover, to differentiate between wild-type and variant ATTR-CM, genotyping are usually completed. If performed, results will be collected.

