### **9.9.3. Patients Lost to Follow-up**

The pragmatic nature of this study (which involves non-intervention on usual patient management practices) may increase the number of patients lost to follow-up after the scintigraphy results reported.

Monitoring on site, remote monitoring and warnings implemented in the e-CRF should minimize this.

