**2. Presence of hereditary (ATTRv) and wild-type (ATTRwt) ATTR**

ATTR patients with a ATTR gene sequencing with variant transthyretin will be considered as ATTRv.

ATTR patients with a ATTR gene sequencing with a result of « No Mutation » will be considered as ATTRwt.

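### The ATTRv/ATTRwt split will describe only the ATTR patients sequenced in routine care, and no planned analysis shows whether the unsequenced differ or how far they could move it

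*SAP*

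**What the plan says.** SAP 2.2 and Protocol section 8 set the objective as the prevalence of ATTRv and ATTRwt in patients diagnosed with ATTR amyloidosis.

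Protocol 9.2.4 says of sequencing: "genotyping are usually completed. If performed, results will be collected". Protocol 9.2.2 and the abstract's list of variables likewise collect genotyping only where available. The background in Protocol section 7 is more ambitious: "A diagnosis of ATTR-CM should be followed by TTR genotyping in all patients".

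SAP 6.3 makes both labels depend on a result. ATTRv needs a variant on sequencing, and "ATTR gene sequencing with a result of « No Mutation » will be considered as ATTRwt". An ATTR patient without sequencing is neither.

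On missing data, SAP 7 says "Missing data will not be imputed". SAP 8.1 says "Qualitative variables will be described using number of filled and missing data" and, for each category, "the frequency and percentage (referring to filled data"), and adds: "A 95% confidence interval (CI) will be associated to binomial proportions using the Wilson score method".

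The endpoint table in SAP 8.2 assigns the split to FAS2 and FAS3 (including 3.1 and 3.2), in patients with positive scintigraphy. The two sensitivity analyses in SAP 8.2 compare periods before and after Amendment 2 for cardiac fixation and for laboratory signs. Neither concerns genotyping.

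Protocol 9.9.3 accepts that the pragmatic design "may increase the number of patients lost to follow-up after the scintigraphy results reported", and adds that monitoring and e-CRF warnings should limit this. The limitations section does not mention selective genotyping.

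**The concern.** Put together, these rules yield ATTRv / (ATTRv + ATTRwt) among patients who happened to be sequenced. That equals the split among all diagnosed ATTR patients only if sequencing is unrelated to carrying a variant. In routine care this cannot be taken for granted, and the plan has no analysis that would show it.

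Two things are at stake. The headline percentage could be shifted, and its interval would give no sign of it. The same sequenced subset also feeds seven further rows of the SAP 8.2 table that are reported within FAS 3.1 by ATTRv and ATTRwt, such as family history, polyneuropathy and carpal tunnel syndrome. If any of those features influences who is sequenced, those rows are affected too.

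The denominator is also unsettled: SAP 8.2 names FAS2 and FAS3, while SAP 2.2 names diagnosed ATTR patients. Dividing by everyone in FAS2 or FAS3 would lower the share.

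**Working it through.** **The plan's own precision figures.** Protocol 9.5 uses N = 1500, ATTR-CM prevalence 10% and a two-sided 95% interval. The half-width is 1.96 × √(p(1−p)/n).
- p = 0.10, n = 1500: 1.52 points (stated 1.5).
- p = 0.30, n = 150 (10% of 1500): 7.33 points (stated 7.3).

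Both reproduce. The second takes all 150 ATTR patients as having data. No precision, genotyping rate or expected share is stated for the ATTRv/ATTRwt split, so every genotyping rate, share and ratio below is an assumption.

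**Direction.** Let π be the true ATTRv share and RR the probability of being sequenced for a variant carrier divided by that for a wild-type patient. The observed share is π·RR / (1 − π + π·RR).

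| RR | π = 10% | π = 20% |
|---|---|---|
| 0.67 | 6.9% | 14.3% |
| 1 | 10.0% | 20.0% |
| 1.5 | 14.3% | 27.3% |
| 2 | 18.2% | 33.3% |

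RR = 1.5 is possible at 70% or 50% genotyped but not at 90%. RR = 2 is possible only at 50%. The share can move either way, and no section gives RR.

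**Size.** Take N = 150 ATTR patients, n genotyped and x variants. The lower bound counts all unsequenced patients as wild-type, x/N. The upper bound counts them all as variant, (x + N − n)/N. The width is (N − n)/N, the ungenotyped fraction.

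| Genotyped | Observed | Wilson 95% | Bounds | Bounds with sampling error |
|---|---|---|---|---|
| 90% | 20/135 = 14.8% | 9.8–21.8% | 13.3–23.3% | 8.8–30.7% |
| 70% | 16/105 = 15.2% | 9.6–23.3% | 10.7–40.7% | 6.7–48.7% |
| 50% | 11/75 = 14.7% | 8.4–24.4% | 7.3–57.3% | 4.1–65.0% |

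The abstract's milestones allow data collection to end at 1000 patients. With 100 ATTR patients, the bounds at 70% genotyped (10/70) are 10.0% to 40.0%, so the picture is the same.

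**What the bounds imply about direction.** Take 21 variants among 105 genotyped, out of 150. The observed share is 20%, Wilson 13.5% to 28.6%. The bounds are 21/150 = 14% and (21 + 45)/150 = 44%. If k of the 45 unsequenced patients carry a variant, carriers are sequenced more often than wild-type patients when 21/(21 + k) > 84/(129 − k). This simplifies to 945 > 105k, or k < 9. The true share is then at least 14% and below 30/150 = 20%. Values above 20% need carriers to be sequenced less often. At the 44% end, 21/66 = 32% of carriers would have been sequenced against 84/84 wild-type patients.

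**The interval.** At the 70% rate, Wilson on 16/105 is 9.6% to 23.3%. With all 150 genotyped at the same share it would be 10.4% to 21.9%. The complete-case interval already widens for the smaller sample. It does not carry the uncertainty about the 45 patients left out.

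**The case against.** A reader might infer that the hereditary share will be overstated, on the view that physicians sequence younger patients and those with neuropathy or a family history. The documents do not support that. They link polyneuropathy to inherited mutations and wild-type disease to older age (Protocol section 7), but nowhere say whom physicians sequence. The exclusion criteria also remove siblings and parents of a known TTR-mutation carrier and anyone with a mutation already found, which takes out part of the group with the strongest family reason for testing.

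A reader might also infer that the Wilson interval is too narrow. As a sampling interval it is sound; it leaves out selection.

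The plan is not silent on missing data. Counts of filled and missing values are reported, and the second Table 15.1.2 shell (FAS 2 and 3) sets ATTRwt and ATTRv beside all of FAS 3.1. The ungenotyped number is visible and part of their age and sex profile can be derived. Genotyping is described as usual practice, and at 90% completeness the effect is modest. The endpoint is secondary and descriptive, and SAP 4.1 makes no inferential claim. Nor is it established that sequencing before Amendment 2 was left to the physician: that amendment deleted biological sample collection, SAP section 1 refers to a centralized laboratory no longer used, and neither document says whether that laboratory did sequencing.

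All of this stands, and it rules out a claim about direction. It does not remove the gap: a count of missing results does not show whether those patients differ, and nothing says how far they could move the share.

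**Conclusion.** The point holds as one of unquantified selection. An objective set for all diagnosed ATTR patients will be answered in a possibly selected sequenced subset, with no formal comparison, bound or sensitivity analysis. The bias may run either way, and its size depends on a genotyping rate that the documents do not give. At an assumed 90% the worst-case bounds span 10 points (13.3% to 23.3%); at an assumed 70% they span 30 points (10.7% to 40.7%). These are extremes, not expected errors. In the 21/105 illustration, the upper end of the 14% to 44% range cannot be cited as evidence of overstatement, since it requires carriers to be sequenced less often. For a descriptive secondary endpoint this is a change that should be made, because it is cheap and alters what can be concluded.

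**What to change.** In SAP 8.2:
- State FAS 3.1 as the population for the split, in line with the objective in SAP 2.2, in place of FAS2 and FAS3.
- Report ATTRv, ATTRwt and not genotyped as three lines over all FAS 3.1 patients, with the genotyping rate.
- Tabulate genotyped against ungenotyped patients on age, sex, ethnic origin, family history and red flags, with completeness for each, since red flags are themselves collected only where available.
- Give the bounds with all ungenotyped patients counted as wild-type and then as variant.
- Extend the before/after Amendment 2 comparison to the genotyping rate and the ATTRv share.
- Label the headline percentage and its Wilson interval as among genotyped patients.

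Inverse-probability weighting can be offered as optional and exploratory, only if the number of variants allows. With perhaps 10 to 20 variants and several predictors it would be unstable.

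The cost is SAP wording and one extra table, using variables the protocol already collects. Nothing changes in patient care or data collection. The price is a less favourable statement of certainty.

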### **9.2.2. Inclusion Criteria**

The study will enroll patients according to the eligibility criteria in participating countries. The recruiting centers will be representative of each country involved in terms of care management systems, of size and of practices (at least when performing feasibility).

To ensure equitable recruitment, each site will be limited to a 100 screened patient maximum.

All patients who met the inclusion and exclusion criteria will be invited to participate in the study.

An informed consent document, will be signed by each patient before any data collection (Appendix 1).

If a patient isn't included in the study for any reason, the non-inclusion register has to be completed (Appendix 2).

The enrollment visit will be performed at the time of inclusion, after the patients' acceptance of enrollment in the study and Informed Consent Document signature.

Data will come from medical records and will be collected in routine clinical practice. The enrollment visit will comprise a first section on patients' eligibility for every patient and a second section on the patient information, family history and clinical evaluation at the inclusion.

After the patient undergoes a Bone Scintigraphy and/or SPECT as part of standard of care (Annex 3) the images will be evaluated by the nuclear medicine specialist of the investigational center.

Scans will be defined at each site according to the internationally accepted grading:

*Grade 0 = absent cardiac uptake*

*Grade 1 = mild uptake less than bone*

*Grade 2 = moderate uptake equal to bone*

*Grade 3 = high uptake greater than bone*

For all patients with cardiac fixation at scintigraphy and/or SPECT the following data will be collected and incorporated in the CRF if available:

- Answers from questions regarding ATTR amyloidosis red flags
- Results from clinical laboratory tests and genotyping.

The patient will finish the study after this visit.

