#### 9.5. Study Size

Considering a prevalence of ATTR-CM around 10%, the screening of N =1500 patients will provide a precision of  $\pm 1.5\%$  in the estimation of this prevalence with a 95% two-sided confidence interval (first objective). In addition, considering such a prevalence, the precision of the estimation of the different symptoms or additional signs within the population of ATTR-CM (other objectives) will be estimated with a precision of  $\pm 7.3\%$  for any sign/symptom with a frequency of 30% or lower.

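### The primary prevalence interval and the stated ±1.5% precision treat patients as independent, and no described analysis uses site or country although patients are clustered in sites that select and grade locally

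*SAP*

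**What the plan says.** Protocol 9.1 describes a multicentre, multinational study that leaves clinical decisions to the participating physicians. Protocol 9.2.2 caps recruitment: "each site will be limited to a 100 screened patient maximum". The same section has each scan read by the nuclear medicine specialist of the enrolling centre, and SAP 2.1 repeats that grading is done at each site.

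The sample size rationale in Protocol 9.5 assumes 10% and 1500 patients and puts the half-width at 1.5 points. It presents this figure as the precision "in the estimation of this prevalence with a 95% two-sided confidence interval". It contains no design effect and no allowance for clustering.

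SAP 8.1 sets the interval method: "A 95% confidence interval (CI) will be associated to binomial proportions using the Wilson score method". It also sets one ordinary logistic model per factor, a 10% screen, then backward elimination at 5%. The covariates in SAP 6.4 begin with "Grade (0, 1, 2, 3) and for grade 2&3 pooled together" and continue with age class, gender, cardiological symptomatology and high creatinine, BNP and NT-proBNP. The subgroups in SAP 5.3 are ATTRv and ATTRwt. The sensitivity analyses in SAP 8.2 compare patients included before and after Amendment 2. Site and country appear in none of these.

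Protocol 9.9.4 accepts that reading of the primary endpoint depends on the evaluator. Of the secondary endpoints it says: "They are also based on symptom assessment that may differ from an investigator to another and may constitute a bias".

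**The concern.** A Wilson interval has its nominal coverage when patients are independent and share one probability of a positive scan. Here, entry requires a planned or recent scan, so each centre's referral habits help decide who is enrolled, and each centre's own reader assigns the grade. Both can make the yield differ between sites. Patients from one site then carry partly the same information, and the simple interval overstates how well the prevalence is known. This matters most for the primary result, on which the study size was based.

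The regressions have two related problems. A factor that varies mainly from site to site, such as how often a sign is looked for and recorded, gets a standard error that is too small. A factor that varies within sites may be confounded if it is also more common where yield is high. Either way, a site difference could pass the 10% and 5% rules and be reported as a red flag.

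**Working it through.** **Inputs from the documents:** prevalence 10%, N = 1500, 95% two-sided (Protocol 9.5); at most 100 patients per site (Protocol 9.2.2), so at least 1500/100 = 15 sites.

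**Assumed inputs:** patients per site m and the ICC. The documents give neither.

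**Step 1: reproduce the stated figure.** 1.96 × √(0.10 × 0.90 / 1500) = 1.52 points. The Wilson interval is 8.58% to 11.62%, also ±1.52. The stated ±1.5% is therefore reproduced with a design effect of 1, that is, with independent patients.

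**Step 2: allow for clustering.** Design effect DE = 1 + (m − 1) × ICC; effective sample size = 1500/DE; half-width = 1.52 × √DE; coverage of the unadjusted interval = 2Φ(1.96/√DE) − 1.

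| m (assumed) | ICC (assumed) | DE | Effective n | Half-width (points) | Coverage of simple 95% CI |
|---|---|---|---|---|---|
| 10 | 0.01 | 1.09 | 1376 | 1.6 | 94% |
| 40 | 0.01 | 1.39 | 1079 | 1.8 | 90% |
| 40 | 0.02 | 1.78 | 843 | 2.0 | 86% |
| 40 | 0.05 | 2.95 | 508 | 2.6 | 75% |
| 100 | 0.02 | 2.98 | 503 | 2.6 | 74% |

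The rows with 10, 40 and 100 per site correspond to 150, about 38 and 15 sites. The last is the extreme in which every site reaches the cap. A beta-binomial simulation at 20, 50 and 100 per site, with ICC 0.02 to 0.10, gave coverage within one percentage point of the formula.

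**Step 3: smaller N.** The protocol abstract also allows data collection to end at 1000 patients. Every half-width is then multiplied by √(1500/1000) = 1.22, and the simple one becomes 1.86 points.

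**Step 4: regressions.** In simulation, a factor with no true effect that varies only between sites was tested at 5% as if patients were independent. Over ICC 0.02 to 0.10 it was significant in 10% to 25% of runs at 20 per site, 17% to 42% at 50, and 26% to 56% at 100. At the SAP's 10% screen the range over the same settings was 16% to 62%. These figures describe purely between-site factors and do not carry over to factors that vary within sites.

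**The case against.** Several counter-arguments have force.

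- **The loss of precision is conditional.** The cap of 100 is a limit, not a typical size, and it restrains dominance by a few sites. With about 10 per site and ICC 0.01 the effect is negligible. This stands: a reader might infer that the interval is certainly too narrow, but the documents do not show that.
- **Tracer is not ignored.** A reader might infer that it never enters the analysis. It is a listed variable (Protocol 9.3). SAP 8.2, Other analyses, item 3 describes all CRF variables by grade in FAS1. Items 5 and 6 make every CRF variable available for both scan results a candidate in the FAS1 regressions. What remains is that tracer is not a planned stratum or adjustment.
- **Not every p-value is affected alike.** P-values that are too small arise mainly for between-site factors.
- **Reader variability is already studied.** External review and weighted kappa are planned (SAP 8.2, item 7), but they measure agreement and do not feed into the prevalence or its interval. The protocol's remarks on laboratories and symptoms concern secondary endpoints, and laboratory variables are excluded from the FAS1 regressions on scan result.
- **Sites are volunteers, not a random sample.** How far to generalise beyond them is a choice. That argues for showing both intervals rather than replacing one.
- **The analysis is exploratory (SAP 4.2).** This softens the regression p-values. It does not excuse poor coverage of the primary estimate.
- **The full table list is a separate document (SAP 9).** A country table may exist there, but the interval method in SAP 8.1 would still be the simple one.

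**Conclusion.** The point holds in conditional form. The primary interval and the stated precision assume independence, and no analysis described in the protocol or SAP takes account of site or country in a design where clustering is plausible. If yield varies by site, the half-width at 1500 patients and 10% prevalence would be about 1.6 to 2.6 points over the assumed combinations in the table, against 1.5 stated. This rests on assumed ICCs and site sizes; the actual effect can be estimated from the study's own data and may prove small. For the regressions, the risk is false positives for between-site factors and confounding by site for within-site factors. This is a worthwhile, low-cost improvement to the plan and does not invalidate the design.

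**What to change.** 1. In SAP 8.1, give the primary prevalence a site-clustered 95% interval beside the simple Wilson one, for example Wilson with n divided by the design effect estimated from the data.
2. In SAP 8.2, add a table of prevalence by country and by tracer with confidence intervals, together with the between-site spread.
3. Add a sensitivity analysis to the FAS1 regressions with a site random intercept or a country term. Do not treat site-clustered robust variance alone as a remedy for confounding: it changes the standard errors and leaves the odds ratios as they were.
4. Exempt the ATTRwt versus ATTRv model. At 10% of 1500 there would be about 150 cases, or roughly 4 per site at 40 patients per site, too few to support site effects.

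The site number is part of each patient's identifier (Protocol 9.2.1) and tracer is recorded, so no new data are needed. The cost is SAP wording, a little more analysis work and possibly wider intervals. If there are few sites (15 is the minimum for 1500 patients), the cluster adjustment will itself be imprecise, so the number of sites should be reported with it.
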